7 days via expired carbon monoxide testing and/or salivary cotinine, 2) obtain a follow-up salivary cotinine level on 100% of children to validate total smoking bans, and 3) complete assessment of outcomes. At 6 months, we will assess all caregivers via phone or email. We may contact them via social media or text messaging as well. Participant's privacy will be maintained when contacting them through social media by sending messages that only the participant can see via social media. PHI will not be used on these messages. Should the caregiver report abstinence and smoking bans, a home visit will be conducted to validate self-reported abstinence and total home smoking bans via salivary cotinine on the child and via expired carbon monoxide testing and/or salivary cotinine on the caregivers during home visits. Follow-ups may be conducted at CCHMC hospital if the participant already has a scheduled appointment at the hospital. If study staff is unable to make contact with the family during the course of the study to schedule the follow-ups an unannounced home visit may be conducted in order to complete study procedures.

Randomization. We will stratify by gender of the primary caregiver and stage of readiness to quit smoking where participants will be in stages 1: pre-contemplation, 2: contemplation 1 or 2, or 3: preparation;^{41,42} thus there will be 8 strata for randomization. A random block randomization scheme will be compiled by the study biostatistician prior to the start of the study, and used by the CRC to allocate participants to each condition. The biostatistician has a SAS® program for creating the randomization scheme that has been tested and used for other studies. As it is anticipated that there will be fewer male caregivers, the random blocks used will be smaller than for the females. The randomization scheme will be accessed by the CRC by logging into a dedicated website and entering the gender and readiness to quit stage, the study group assignment and a study identification number will be returned. Backup will be opaque envelopes, kept within the PED with stratification and study identification number marked on the outside.

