Delivery of the SBIRT and HHC. Six or more clinical counselors/intake coordinators/research coordinators will be available in the PED to deliver the SBIRT and HHC⁴³ [ENREF 65](#) interventions. The use of clinical counselors/intake coordinators/research coordinators will increase the generalizability of the intervention, as most U.S. emergency departments have clinical counselors/intake coordinators/research coordinators available.

Resources for quitting marijuana use: Should participants report that they are current marijuana users, they will be offered information to help them quit marijuana use.

Setting. This study will occur in the main PED or in the Urgent Care of CCHMC.

Clinical Counselor/Intake Coordinator/Research Coordinator Activities, Training, and Monitoring

Three or more clinical counselors/intake coordinators/research coordinators will deliver the SBIRT intervention and three or more clinical counselors/intake coordinators/research coordinators will deliver the HHC intervention to caregivers while their child is waiting to be seen in the PED. All clinical counselors/intake coordinators/research coordinators will receive formal motivational interviewing (MI) training from an MI expert. This training, followed by booster session(s) after approximately 6 months or more, will teach them how MI can be used as a collaborative, person-centered form of guiding to elicit and strengthen motivation for change and will help them use specific skills related to MI. Clinical counselors/intake coordinators/research coordinators will be trained in MI strategies and techniques. The MI trainer will review a selection of audio recordings of each clinical counselor/intake coordinator/research coordinator chosen randomly throughout the study period and they will receive individualized feedback on these sessions from the MI trainer. The reviews will be spread out over the course of recruitment period. The clinical counselors/intake coordinators/research coordinators' audio-recorded sessions will be independently rated for adherence using the Motivational Interviewing Treatment Integrity (MITI) system by our MI expert, who will provide individualized written and verbal feedback to each clinical counselor/intake coordinator/research coordinator.⁴⁴ These audio-recorded sessions will be collected in an ongoing basis to facilitate fidelity to MI. MI approaches have been successfully applied in the ED setting for a variety of issues, including alcohol and smoking.⁴⁵

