1) NRT: All caregivers who do not have any contraindications to NRT will be offered a free, 6 week supply of their choice of NRT patches or lozenges. NRT will be stored in a locked cabinet in the CRC office in the PED. The clinical counselors/intake coordinators/research coordinator will screen all participants for eligibility and for any contraindications to NRT using a screening checklist (See Appendix F). If there are any questions about eligibility for NRT, the clinical counselors/intake coordinators/research coordinators will contact the PI or other study MD. The PI or other study MD will be available in-person or by phone to address any questions. This arrangement has worked well for our most recent cessation trial (5K22CA163747). The screening checklist will be sent electronically to the PI or other study MD if there are any contraindications to NRT, who will approve/disapprove the distribution of NRT to the caregiver. If there are no contraindications to NRT on the checklist, the form will not be sent to the PI or other study MD, and the research coordinator may dispense NRT to the caregiver. Study staff will instruct the caregiver on NRT use and they may use expired NRT to demonstrate to caregivers how to place the patch on and to show them what the lozenge looks like. In addition, all caregivers will be provided a home visit for follow-up at 6-weeks during which they will be asked if they were given NRT at baseline, and if so, if they used the NRT. If they used approximately 80% of the NRT and wish to receive more NRT, they will be screened for eligibility and for any contraindications to NRT using the screening checklist in the same manner listed above as at baseline (See Appendix I). If eligible, they will receive 6 weeks of NRT. If a home visit is not possible, the survey will be completed via phone or email and the sample may be obtained from the family via mail. An approximately four week window for follow-up will be used. The follow-up may also be completed at CCHMC or another mutually agreed upon location, if the participant has an already scheduled appointment.

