During the approximately 48-month or longer study enrollment period, CRCs and approximately 1-2 pairs of clinical counselors/intake coordinators/research coordinators (i.e., one from each condition) will provide study coverage every weekday. This increases the opportunities for recruitment and delivery of the interventions. Our prior research demonstrates that approximately 3 CRCs will be more than adequate to recruit 750 caregivers. Enrollment times will represent peak PED volumes. CRCs will screen consecutive caregivers of patients presenting to the PED using CCHMC's EMR system, Epic. CRCs will identify caregivers by reviewing Epic records of registered patients. A secure database will be used which will include all patients, their age, gender, race, chief complaint, enrollment status, and reasons for non-enrollment.

Eligible caregiver adult participants must: 1) be > or equal to age 18; 2) be accompanying a child 0-17 years of age 2) be a daily smoker; 3) speak and read English (if shown to be efficacious, we will translate the intervention materials and test it with multi-lingual CRCs and clinical counselors/intake coordinators/research coordinators in a future trial), 4) have a permanent address and a working cell or landline number, 5) live within an approximately 50 mile radius of CCHMC (since we will conduct home visits.)

Eligible child participants must: 1) Not be a current smoker of tobacco or marijuana; 2) present to the PED with : (a) a stable condition, that is, patients who are not critically ill and do not require immediate treatment and intervention by the PED practitioner (triage levels 2-5) and (b) a potentially SHSe-related complaint (which will include complaints such as wheezing, difficulty breathing, cough, ear infection, cold, ear pain, runny nose, congestion, flu, asthma, shortness of breath) as outlined by the U.S. Surgeon General;⁴⁸ or SHSe-related discharge diagnosis.

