Data Collection and Participant Retention. All baseline assessments will be electronically sent to a central, secure, HIPAA-compliant firewalled CCHMC database. We will use multiple strategies to retain the sample by relying on approaches successfully used by our PI and Co-Is in studies of high-risk, low income populations.⁶¹⁻⁶⁵ These strategies include: 1) Generous incentives:¹⁵ [ENREF 92](#) Participants will be paid with increasing compensation of \$30 at baseline, \$50 at 6-weeks (\$20 for phone assessment and \$30 for home visit), and \$65 at 6-months (\$30 for phone assessment and \$35 for home visit); 2) Conducting home visits on all caregivers and children at the 6-week follow-up to assess outcomes and giving caregivers in the SBIRT group an additional 6 week supply of NRT if they have used approximately 80% of the NRT provided at baseline; 3) Hiring and training CRCs to carefully track participants, make home visits, and obtain follow-up data by making as many follow-up attempts as is necessary to locate participants; 4) Sending caregivers: weekly email/mail/text messages with cessation or healthy habits tips for 12 weeks, reminders of upcoming assessments. We will ask order of preference of type of reminders and follow-up; however if one technique is unsuccessful, the second and finally third choice will be used; 5) Branding study contact information in reminder postcards; 6) Collecting contact information of friends and family members completed at baseline that will contain contact information for the participant and their contacts. Cell phone numbers, e-mail addresses, and preferred times of contact will be obtained; 7) Asking our on-site Co-I ([name]) to provide strategies to maximize retention through thorough tracking and monitoring of study participants. 8) Study staff will attempt to contact participants via phone, text, email or traditional mail in order to complete the follow-ups. In the event that a research participant becomes lost to follow-up and traditional re-contact methods (i.e. telephone, text, email, traditional mail, etc.) are unsuccessful, the use of a nationwide electronic search strategy will be employed. This will include general use of public web-based search functionality, and as a last resort, the use of a 3rd party service (Accurint). Accurint will be administered through a centralized standard process managed by the CCHMC *Center for Clinical and Translational Science and Training (CCTST)*. Only demographic information will be utilized for the purpose of facilitating the Accurint search function. Specific individual requests will be submitted to a designated member of the CCTST staff that will perform the search using the Accurint functionality. CCTST staff will provide a report back to the research team that includes the most current available contact information for the requested research participant(s). Records of each search will be maintained and available for IRB review if needed.

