and dermal transfer. These thirdhand tobacco smoke exposure, thirdhand marijuana smoke exposure and pollution levels can be assessed by analyzing urine, and hand wipes of children and by analyzing dust and surface wipe samples from the home. Sometimes these samples can also be used to analyze secondhand smoke exposure levels as well. Thus, we may collect: 1) saliva samples from all children and hand wipe samples of all children during the baseline visit, 2) urine samples from all children who can easily urinate into a cup or bag or who urinate in a diaper if there is time during the baseline visit, 3) hand wipe samples of all children during the 6-week home/other location visit, 4) urine samples from all children who can easily urinate into a cup or bag or who urinate in a diaper if there is time during the 6-week visit, 5) home dust samples and surface wipe samples and air samples from all home visits at 6-weeks if the CRC goes to the home, 6) hand wipe samples of children that have home/other location visits at 6 months, 7) home dust samples and surface wipe samples and air samples from any home visits at 6-months if the CRC goes to the home, 8) urine samples from all children who can easily urinate into a cup or bag or who urinate in a diaper if there is time during any 6-month visits; 9) cheek swabs from the caregiver and the child at six weeks and at six months, 10) home surface area measurements. Urine collection kits may be given to participants at any of the study time points and may be mailed to, given to, or collected from participants before or after follow-up visits. Urine that is collected by participants may be either refrigerated or frozen by the participants prior to collection by study staff and delivery to the CTRC. These biological and environmental samples will be stored in the CTRC and may be analyzed for thirdhand tobacco smoke, secondhand and thirdhand marijuana smoke exposure. Once sample analyses are completed, we may examine how SHS and THS tobacco and/or marijuana levels are associated with data that may include child demographics, caregiver tobacco and/or marijuana use, home characteristics, child clinical findings, disposition, and child healthcare visits once funds become available. Participants may opt out of having their samples analyzed for marijuana smoke exposure. Participants who were consented prior to version 11 of the protocol may be re-consented at follow-up in order to use these samples for marijuana smoke exposure analyses. If the follow-up visits do not occur in the participant's home, then dust samples will not be obtained; although participants who do not have a home visit will be asked to bring a vacuum bag, if available. When funds become available, biological and environmental samples from participants and their homes will be sent to the Measurement & Evaluation Research Group (MERG) at San Diego State University Research Foundation for analysis. The San Diego State University site will be given information that may include data such as: type of specimen, study ID number, portions of baseline and follow-up assessments (including sociodemographics), and measurements and description of the area of the home sampled. Leftover samples will be returned to CCHMC. A Materials Transfer Agreement is in place which details these procedures.

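### The plan does not blind outcome assessors to arm or place the outcome questions before the NRT step at the 6-week visit, leaving self-reported prolonged abstinence and smoking bans open to arm-aware questioning

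*Combined protocol and SAP*

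**What the plan says.** Allocation. Under Randomization, the scheme is "used by the CRC to allocate participants to each condition". The mechanism is explicit: "The randomization scheme will be accessed by the CRC by logging into a dedicated website and entering the gender and readiness to quit stage", after which "the study group assignment and a study identification number will be returned". The CRC therefore sees the arm.

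Follow-up. Under Data Collection and Participant Retention, one retention strategy is "Hiring and training CRCs to carefully track participants, make home visits, and obtain follow-up data". The item on secondhand and thirdhand smoke samples also has the CRC as the home visitor: "home dust samples and surface wipe samples and air samples from all home visits at 6-weeks if the CRC goes to the home". On team size, Participant Screening, Enrollment, and Exclusion says: "Our prior research demonstrates that approximately 3 CRCs will be more than adequate to recruit 750 caregivers".

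NRT at the outcome visit. The SBIRT Protocol (Assist, NRT) describes the 6-week home visit as one "during which they will be asked if they were given NRT at baseline, and if so, if they used the NRT". Those who used about 80% and want more are screened and resupplied. The retention section confines this resupply to the SBIRT group, and the study supplies NRT in no other arm.

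Blinding. The only blinding described is for the raters of audio-recorded sessions, in the section on counselor training and monitoring.

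Measurement. Follow-up Assessments calls prolonged abstinence a self-report measure and point prevalence biochemically validated. The item on child SHSe defines a complete ban by caregiver report. Biochemical Validation sets a carbon monoxide limit of 6 ppm for caregivers, with cotinine as a back-up, and has child saliva assayed by an outside laboratory.

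**The concern.** SBIRT caregivers are urged to quit and to ban smoking at home and in the car; HHC caregivers receive diet and activity advice. An interviewer who knows the arm may word, probe or accept answers about smoking differently, even without meaning to. Under the plan as written, the interviewer may know the arm in two ways: from having obtained the allocation, or from the NRT conversation at the visit.

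This matters most for outcomes that rest on what the caregiver says. Prolonged abstinence is a primary outcome with a planned control rate of only 2.1%, so a handful of extra reports in one arm is a large relative change. Reported bans are a main outcome of Primary Aim 2.

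**Working it through.** **Step 1: can the assessor know the arm?** The assignment is returned to the CRC, CRCs do the follow-up, and about three CRCs are foreseen for recruiting 750 caregivers. With so few people, the one who allocated a caregiver can readily be the one who visits. At 6 weeks, a caregiver who says the study gave her NRT is identified as SBIRT. A denial points to HHC but does not prove it, since SBIRT caregivers with contraindications, or who are pregnant or nursing, receive none. At 6 months no NRT step is described, so the concern there rests on the CRC's earlier knowledge.

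**Step 2: which outcomes are exposed?**
- Prolonged abstinence: self-reported, so exposed. Purpose says the primary outcomes are validated in all participants, but Follow-up Assessments attaches validation to point prevalence, and no rule says that a failed test reverses a report of prolonged abstinence.
- Home/car bans: defined by report, so exposed. Child cotinine is compared between families with and without a reported ban, but no cut-point overrides the report.
- Point prevalence: partly protected, because those reporting abstinence are to be tested. The HHC Protocol lets assessments fall back to phone or email, which can lose the test.
- Child cotinine: largely protected, being a laboratory assay.

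**Step 3: sensitivity calculation.** The plan gives no figure for reporting bias, so there is none to reproduce. Inputs from Sample Size and Power Estimates: 300 per arm after 20% loss; prolonged abstinence 2.1% in HHC and 7% in SBIRT. Assumptions: two-sided 5% level (the plan states neither level nor sidedness); no true effect; a net share *b* of SBIRT non-abstainers reporting abstinence over and above HHC.

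Formulas, with p1 = 0.021:
- p2 = p1 + b(1 − p1), d = p2 − p1, p̄ = (p1 + p2)/2
- s0 = √[2p̄(1 − p̄)/n], s1 = √[(p1(1 − p1) + p2(1 − p2))/n]
- P(reject) = 1 − Φ[(1.96·s0 − d)/s1] + Φ[(−1.96·s0 − d)/s1]

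Example, b = 3%: p2 = 0.021 + 0.03 × 0.979 = 0.0504; d = 0.0294; s0 = 0.01515; s1 = 0.01510. Then (1.96 × 0.01515 − 0.0294)/0.01510 ≈ 0.02, and P(reject) ≈ 0.49.

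The caregiver column is b × 300 × 0.979.

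| b (assumed) | Extra SBIRT caregivers of 300 | Observed SBIRT rate | P(significant difference) |
|---|---|---|---|
| 0% | 0 | 2.1% | 5% |
| 1% | 2.9 | 3.1% | 12% |
| 2% | 5.9 | 4.1% | 28% |
| 3% | 8.8 | 5.0% | 49% |
| 5% | 14.7 | 7.0% | 82% |

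At 5% the observed SBIRT rate equals the planned 7%, so about 15 such reports would imitate the whole planned effect.

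Bans are less sensitive. With the same method and the plan's HHC range of 50% to 65%, 5% net over-reporting gives 9% (base 50%) to 7% (base 65%); 10% gives 23% to 15%.

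**The case against.** - **Caregivers know their arm.** In a counselling trial this cannot be avoided, and over-reporting from it would persist with a fully blinded assessor. This stands. A reader might take the table as the harm done by unblinded assessors; it is not. It covers net over-reporting from any cause, and the assessor's share is unknown.
- **Validation limits the damage.** This stands for point prevalence and child cotinine, and a 6-month claim of quitting is itself what triggers a test. A reader might repeat the calculation at the 6.3% point-prevalence rate, where 3% and 5% over-reporting give 25% and 53%. Those figures assume that no false report is removed by testing, whereas that outcome is biochemically validated. Nor can one say that every outcome of Aims 1 and 2 is compromised.
- **Counsellors need not be assessors.** Delivery staff are described thus: "Six or more clinical counselors/intake coordinators/research coordinators will be available in the PED to deliver the SBIRT and HHC". Because research coordinators are in that list, a reader might infer that a caregiver's own counsellor collects her outcomes. The SBIRT and HHC protocols name CRCs separately from delivery staff. Other text blurs the line: the risk section has a trained CRC screening for NRT eligibility, and the control rationale speaks of contact time with the CRC. The overlap is unclear and should not be asserted.
- **The forms may already set the order.** The six-week assessment and six-week NRT checklist are separate appendices whose content is not shown. They might put outcomes first; the protocol text does not require it.
- **Three CRCs were judged adequate for recruitment, not for blinded home visits.** This is fair, so separating staff can only be asked for where scheduling allows.

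**Conclusion.** The concern holds in a limited form. As written, the plan permits arm-aware collection of self-reported prolonged abstinence and caregiver-reported bans. Lack of assessor blinding is inferred from the procedures and from silence; the documents do not state it outright.

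Its size cannot be derived from the documents. The sensitivity figures (12% to 82% false positives for 1% to 5% net over-reporting of prolonged abstinence) rest on assumed over-reporting shares, no true effect, 300 per arm and a two-sided 5% test. They show how little differential reporting a 2.1% outcome can absorb, not how much will occur. The change is worth making because it is cheap, although the part due to caregivers' own knowledge will remain.

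**What to change.** 1. Order the 6-week REDCap form so that abstinence and ban items, the carbon monoxide reading and the child saliva sample are completed and locked before any NRT-use question or resupply step opens. This concerns the order of data collection only and changes nothing about who is resupplied.
2. Wherever possible, have caregivers complete the abstinence and ban items themselves through the participant-specific REDCap survey link already provided for under Confidentiality/Security.
3. Where scheduling among existing CRCs allows, assign follow-up to a CRC who did not enrol or allocate that caregiver, working from a visit list without the arm. Record whether the arm became known before the lock.

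The cost is a reordered form, a short amendment and some scheduling effort, with no new staff. The downsides are some loss of continuity between caregiver and CRC, and the need to arrange for NRT to be at hand without showing the arm before the lock. If follow-up is already under way, the sponsor can still report who assessed whom and in what order.
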